8.4.2.2 Short form 36-item (SF-36) domain and composite scores

The SF-36v2, standard recall, measures the following eight health domains as rated by the subjects over the past four weeks: Physical Functioning, Role Physical, Bodily Pain, General Health, Vitality, Social Functioning, Role Emotional, and Mental Health. The classification of the questionnaire items to the health domains is shown in Section 13.7.

The SF-36 PCS and MCS scores are used to measure the two broad components, or aspects, of health-physical and mental. PCS and MCS are based on the aggregate of the eight health concepts described above and all of the eight health domain scales are used to score both components summary measures.

One additional item asks responders about health change over the past year.

The SF-36 will be used using QualityMetric's Health Outcomes™ Scoring Software. The software uses updated 2009 U.S. population norms and applies a Full Missing Score Estimation (Full MSE) method as follows

- A health domain score (except the PF domain) will be estimated provided that at least one non-missing response is available within that domain
- For the PF domain item, response theory will be used to develop a model for estimates of the missing score
- Regression methods are then applied to estimate the PCS and the MCS on the basis of the available domains.

A by-participant listings of SF-36 item responses will be provided. Missing data will not be imputed.

8.4.2.3 ITP-PAQ Domain Scores

The ITP-PAQ V1 consists of 44 items that comprise 10 scales. Each of the 10 scales is scored 0 to 100 according to formula shown in section 13.5, with higher scores indicating better quality of

life. Four of the scales measure physical health: Symptoms, Bother, Fatigue, and Activity. Two of the scales measure emotional health: Fear and Psychological Health. The remaining four scales measure other aspects of QOL: Work QOL, Social QOL, Women's Reproductive QOL, and Overall QOL.

A by-subject listing of the ITP-PAQ V1 questionnaire, ITP-PAQ V1 item responses will be provided by treatment group.

8.4.3 Hospitalization due to ITP / Number and length of hospitalizations

Hospitalizations will be listed.

8.4.4 Effect of Rozanolixizumab on Patient Reported Outcomes (PRO)

8.4.4.1 FATIGUE-PRO physical fatigue score

The Fatigue Patient Reported Outcome (PRO) physical fatigue scale consists of 9 items. The scale is 1 out of the 3 scales composing the broader Fatigue instrument developed by UCB. Items are rated within a 7-day recall period on a 5-point Likert frequency scale ranging from "none of the time" to "all of the time."

A by-subject listing of the FATIGUE-PRO items will be provided by treatment group.

8.4.4.2 Patient Global Impression of Severity (PGI-S)

The PGI-S consists of a single-state, self-report measure that rates a study participant's severity of specific condition, depicting a study participant's rating of overall symptoms ("none", "mild", "moderate", "severe", or "very severe").

A by-subject listing of PGI-S will be provided by treatment group.

8.4.4.3 Patient Global Impression of Change (PGI-C)

The PGI-C is a single-state, self-report measure that reflects a study participant's belief about the efficacy of treatment for a specific condition. The PGI-C is a 7-point scale depicting a study participant's rating of overall improvement ("very much improved," "much improved," "minimally improved," "no change," "minimally worse," "much worse," or "very much worse"), was planned to be summarized at all available post-baseline visits using descriptive statistics by treatment group on the RS.

A by-subject listing of PGI-C will be provided by treatment group.

The PGI-C sample questionnaire is available in the protocol, Appendix 18, Section 10.18.

9 PHARMACOKINETICS (PK) AND PHARMACODYNAMICS (PD)

9.1 Pharmacokinetics

Individual plasma concentration of rozanolixizumab will be summarized by scheduled sampling day for the PK-PPS using n, arithmetic mean, median, SD, minimum, maximum, geometric mean (geomean), geometric coefficient of variation (geoCV) and 95% CI (assuming log-normally distributed data) up to week 4.

The following rules will apply for PK data listings and summaries:

-
- Values below the LLOQ will be reported as below the limit of quantification (BLQ)
 - Descriptive statistics of concentrations will be calculated if at most 1/3 of the individual data points at a timepoint are missing or are not quantifiable (<LLOQ). Values that are BLQ will be replaced by the numerical value of the LLOQ/2 in this instance.
 - The 95% CI lower and 95% CI upper should be left blank if the SD (or equivalently, the geoCV) is 0
 - The geoCV will be calculated using the following formula where SD is the standard deviation from the log-transformed data

$$\text{geoCV (\%)} = \text{sqrt}[(\exp(\text{SD}^2) - 1)] \times 100$$

Individual concentrations of rozanolixizumab will be listed for the RS for each individual with the actual time and will include the equivalent dose and actual dose being administered previous to the pk sample, the sampling time in days relative to the previous dose, the IgG observed at the same visit, the ADA titer observed for the binding assay and the NAb titer for the same visit and platelet count for the corresponding visit.

9.2 Antidrug antibodies (ADA)

The immunogenicity analysis should be done on the safety set SS. Samples from study participants on placebo will not be tested for anti-drug antibodies.

Anti-rozanolixizumab antibodies will be measured using a three-tiered assay approach: screening assay, confirmatory assay and titration assay. Samples will first be evaluated in the screening assay (reported as 'negative screen' or 'positive screen'), followed by analysis of screened positive samples in the confirmatory assay to confirm the true positivity of the samples (reported as 'negative immuno-depletion' or 'positive immuno-depletion'). Samples that are confirmed as positive in the confirmatory assay will be evaluated in a titration assay to quantify the ADA level and will be reported as titer (reciprocal dilution factor including minimum required dilution (MRD)). Any sample confirmed positive for ADA within the confirmatory assay will be further evaluated for the presence of neutralizing anti-rozanolixizumab antibodies.

Screening, confirmatory, and titer cut points of the respective assays will be determined by the bioanalytical laboratory. The relevant statistical reports will be provided as part of the bioanalytical reports. Rozanolixizumab has the potential to interfere with the antibody assay at concentrations above the drug tolerance limit (DTL); therefore, an integrated evaluation of anti-rozanolixizumab antibody results and rozanolixizumab plasma concentration will be used to enable the interpretation of immunogenicity results. The ADA sample status will be determined for each visit where samples were taken for ADA analysis:

- Sample values that are either 'negative screen' or the combination of 'positive screen' and 'negative immunodepletion', will be defined as ADA negative if corresponding rozanolixizumab concentrations are equal or below the validated drug tolerance limit of the ADA assay (██████████ rozanolixizumab) allowing detection of 100ng/mL ADA
- Sample values that are either 'negative screen' or the combination of 'positive screen' and 'negative immuno-depletion', but with corresponding rozanolixizumab

concentrations above the validated drug tolerance limit of the ADA assay, will be defined as ADA inconclusive

- Sample values that are ‘positive screen’ and ‘positive immunodepletion’ will be defined as ADA positive
- Samples that could not be tested for ADA status due to inadequate sample volume, mishandling, or errors in sample collection, processing, storage, etc., will be defined as Missing
- Neutralizing antibody (NAb) sample status (positive/negative/missing) will be determined for ADA positive samples. Samples that are NAb positive will be evaluated in a titration assay to quantify the NAb level and will be reported as titer.

The ADA participant status will be classified on individual and group level as outlined below (Shankar et al. 2014; Rup et al, 2015). A description of how study participants will be categorized for the immunogenicity assessment is provided in [Table 9-1](#).

Individual study participants will be assessed for ADA participant status, composed of 6 categories: ADA negative, inconclusive, and ADA positive, whereby a positive participant’s status is determined as originating from a treatment-induced, boosted, reduced or unaffected ADA response.

Study participants who are identified as being treatment-induced or treatment-boosted ADA-positive will be grouped as treatment emergent (TE)-ADA positive participants. Study participants who are identified as being treatment-reduced or treatment-unaffected ADA-positive will be grouped as non-TE-ADA positive participants. Both TE-ADA positive and non-TE-ADA positive participants will be further classified as NAb negative or NAb positive.

The individual and combined ADA participant categories will be summarized overall through the SFU sample if applicable (timepoint of interest). The ADA categories are defined in [Table 9-1](#) below.

Notes:

- The ADA sample status should be determined for each visit where samples were taken for ADA analysis.

ADA Baseline

By default, the Day 1 will be the Baseline value if the ADA status at screening is ADA negative or missing. If the ADA status at screening is ADA positive and ADA status at Day 1 is ADA negative or missing, the screening will be the Baseline value. If the ADA status at screening and Day 1 are same, Day 1 will be the Baseline value.

Table 9-1: Terms and Definitions for ADA Status Evaluation in Study Participants

Term	Definition	Category
Individual participant categories		
Pre-ADA negative – treatment induced ADA negative (ADA-NEG)	Study participants who have an ADA negative sample at Baseline and at all sampling points post-Baseline up to the timepoint of interest.	1
Inconclusive	Study participants who have an ADA positive or negative Baseline sample and some post-Baseline samples are missing or inconclusive, while other post-Baseline samples are ADA negative up to the timepoint of interest.	2
Pre-ADA negative – treatment induced ADA positive (TI-POS)	Study participants who have an ADA negative sample at Baseline and at least one ADA positive sample at any sampling point post-Baseline up to the timepoint of interest	3
Pre-ADA positive – treatment boosted ADA positive (TB-POS)	Study participants who have an ADA positive sample at Baseline and at least one ADA positive sample at any sampling point post-Baseline up to the timepoint of interest with increased titer values compared to Baseline (greater than a predefined fold difference increase from Baseline value which will be defined within the validation of the assay ie MSR of the assay ¹)	4
Pre-ADA positive – treatment reduced ADA positive (TR-POS)	Study participants with an ADA positive sample at Baseline, and ADA negative samples at all sampling points post-Baseline up to the timepoint of interest	5
Pre-ADA positive – treatment unaffected ADA positive (TU-POS)	Study participants with an ADA positive sample at Baseline and an ADA positive sample at any sampling point post-Baseline up to the timepoint of interest, with titer values of the same magnitude as Baseline (less than a predefined fold difference from the Baseline value which will be defined within the validation of the assay, ie MSR of the assay ¹)	6
Combined participant categories		
Treatment emergent ADA positive (TE-POS)	Includes study participants who are treatment induced ADA positive (category 3) or treatment boosted ADA positive (category 4).	7
Non-treatment emergent ADA positive (Non-TE-POS)	Includes study participants who are treatment reduced ADA positive (category 5) or treatment unaffected ADA positive (category 6).	8

Table 9-1: Terms and Definitions for ADA Status Evaluation in Study Participants

Term	Definition	Category
Treatment emergent ADA positive – NAb positive (TE-POS, NAb-POS)	Includes study participants who are treatment emergent positive (category 7) and have at least one NAb positive sample	9
Treatment emergent ADA positive – NAb negative (TE-POS, NAb-NEG)	Includes study participants who are treatment emergent positive (category 7) and have no NAb positive samples	10
Non-treatment emergent ADA positive - NAb positive (Non-TE-POS, NAb-POS)	Includes study participants who are non-treatment emergent positive (category 8) and have at least one NAb positive sample	11
Non-treatment emergent ADA positive - NAb negative (Non-TE-POS, NAb-NEG)	Includes study participants who are non-treatment emergent positive (category 8) and have no NAb positive samples	12

¹The fold difference increase from baseline value, ie the minimum significant ratio (MSR) determined during assay validation, will be reported in the relevant tables, listings and figures. It reflects the fold difference in titer level that considered higher than the assay variation in titer determination.

The following outputs will be created:

Summaries on the SS:

Tables:

- Number and percentage of participants in the RLZ arm with positive, negative, inconclusive or missing sample ADA status at the time of each visit will be summarized overall. Denominator is the number of study participants having a non-missing result at that visit.
- Number and percentage of participants in the RLZ arm in each of the ADA individual categories (1 to 6) and combined (7-12) presented above will be summarized overall. Denominator will be the total number of study participants having an individual ADA participant category defined
- Summary tables displaying the total prevalence of pre-existing ADA and NAb, and persistent ADA positivity in the RLZ arm, as defined below:
 - Total prevalence of pre-existing ADA and NAb: number and percentage of participants having an ADA positive sample status at baseline, with the denominator being the total number of study participants having a non-missing sample result at baseline. The same will be repeated for NAb.
 - Persistent ADA positivity: Number and percentage of study participants with treatment-induced ADA positive samples detected at 2 or more sequential sampling time points during the treatment (including observation and off-treatment periods), where the first and last ADA positive samples are separated by at least 16 weeks (equal to 5 half-lives of human IgG [22 days], as per Rup et al., 2015).

Listings:

Listings by timepoint using the SS will be created. The following datapoints will be included:

- Rozanolixizumab concentration
- Total IgG, and absolute platelet counts
- ADA screening results (with the confirmatory result, the ADA titer result if applicable and the ADA sample status)
- NAb result titer (when performed)
- Time since administration of IMP (in days)
- Individual ADA participant classification that apply (as defined above)
- Previous visit actual dose (mg/kg equivalent) and actual dose (mg)
- By-subject listing of immune-Related TEAEs, TEAEs of hypersensitivity reaction, anaphylactic reaction, injection site reaction, or autoimmune disorder anti-drug antibodies, the time of onset, the ADA and NAb sample status and ADA and NAb titers at the closest sampling time point prior to and subsequent to the TEAE, and time since last administration of IMP (in days).
- Notes: Study physician/safety physician/safety lead will mark the Preferred Term of immune related AEs based on an excel output of all TEAEs (blinded) after database lock. The marked AEs will be used for the summary.

9.3 Pharmacodynamic endpoints (PE)

The following pharmacodynamic endpoints will be based on the SS.

9.3.1 Total serum IgG (absolute value) and change from Baseline (absolute value and percentage) in serum IgG and in serum IgG subclass concentration at each scheduled assessment

Total serum IgG concentrations will be summarized and listed on the SS by time point for absolute values, change from Baseline, and percentage change from Baseline overall and stratified by body weight tier.

IgG subclasses will be listed on the SS by treatment group, and time point for absolute values, change from Baseline, and percentage change from Baseline overall

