6.4.2 Prohibited concomitant treatments (medications and therapies)

The following concomitant medications are prohibited during the study:

- IVIg (unless given as a rescue therapy)
- All biologics including rituximab
- Cyclophosphamide
- Pimecrolimus
- PEX
- Immunoabsorption

- Anti-D
- Any systemically administered corticosteroids above the allowed background dose (unless required as a rescue therapy)
- Romiplostim
- Vinca alkaloids (vincristine, vinblastine)
- Anticoagulants and antiplatelets (warfarin, heparin, clopidogrel, aspirin [enteric coated up to 150mg daily allowed], salicylics, dipyridamole, prasugrel, ticagrelor, tirofiban, and abciximab).

For study participants who require a medical or surgical procedure that requires the use of general anesthesia, discussion must occur prior to the procedure with the Medical Monitor or study physician, such that a decision on the participant's continued participation in the study can be made. In an emergency situation, the discussion should occur as soon as possible after the procedure.

The use of prohibited concomitant treatment will lead to permanent discontinuation from IMP. Study participants should then complete the assessments outlined for the Early Withdrawal (EW) Visit and enter the SFU Period.

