6.4.3 Rescue therapy

Rescue treatment will be given as per standard of care and at the discretion of the investigator as described below. If such rescue therapy is given, the participant is allowed to continue IMP treatment (as per guidance below), and should continue to complete all remaining scheduled visits in the Treatment Period, as per the Schedule of Activities (Section 1.3). The following rescue therapies may be used:

- Any increase in concomitant ITP therapies above Baseline dose
- Any additional ITP medication/therapies including but not limited to:
 - Platelet transfusion (only in cases of severe bleeding)
 - Commercially available IVIg
 - Any systemically administered corticosteroids (above the background doses, ie, pulse, oral and iv steroids). Any systemic corticosteroids used for the management of infusion reactions or other medical conditions are also considered rescue therapy.
 - Immunosuppressants (except for those listed in Section 6.4.2).

Although the use of rescue therapy is allowable at any time during the study, the use of rescue therapy should be delayed, if possible, for at least 2 days following the administration of study treatment.

If IVIg, high dose corticosteroids, or platelet transfusion are given as rescue therapy, IMP treatment can commence at the same dose as previously when platelet counts are $<50 \times 10^9/L$. Dose can be up-titrated at a later timepoint, if needed, depending on platelet level.

A high dose of corticosteroids is defined as any iv administration of corticosteroids given for any reason or doubling of an oral dose resulting in a dose more than 20mg/day prednisone equivalent dose.

In case of an increase of Baseline oral corticosteroids, not resulting in doubling of the oral dose more than 20mg/day prednisone equivalent dose, an increase in the concomitant ITP therapies above Baseline, or in case of administration of immunosuppressants as rescue therapy, IMP administration can continue as per Schedule of Activities (Section 1.3) at a dose adjusted depending on the platelet level.

The date and time of rescue therapy administration as well as the name and dosage regimen of the rescue therapy must be recorded in the eCRF.

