9.1 Definition of analysis sets

- Enrolled Set: All study participants who have signed the informed consent.
- Randomized Set (RS): All enrolled study participants who were randomized. This is equivalent to the Intent-to-Treat Set.
- Safety Set (SS): All randomized study participants who received at least one dose of IMP (partial or full). Analysis of this set will be according to the treatment the participants actually received and will be used for the demographic and safety analyses.

The analysis of the PD (excluding total IgG, and IgG subclasses) and immunologic variables will be performed on the SS. Selected outputs may be repeated for the PD Per-Protocol Set (PD-PPS). Further details will be provided in the SAP.

- Full Analysis Set (FAS): Consists of all study participants randomized who have received at least one complete sc infusion of IMP, have a valid Baseline, and at least 1 valid post-Baseline platelet count measurement during Weeks 13-25.
- Pharmacodynamic Per-Protocol Set (PD-PPS): A subset of the SS, consisting of those study participants who had no important protocol deviations potentially affecting the serum concentration of total IgG, as confirmed during a pre-analysis review of the data prior to database lock. Protocol deviations may not necessarily lead to total exclusion of a participant from the PD-PPS but may lead to exclusion of specific data.
- Pharmacokinetic Per-Protocol Set (PK-PPS): A subset of the SS, consisting of those study participants who received at least 1 dose, had at least 1 valid PK measurement, and no important protocol deviations affecting the PK variable, as confirmed during a pre-analysis review of the data prior to database lock.

The RS will be the primary analysis set for efficacy analyses.

The PD-PPS will be used for the analysis of the total IgG, and IgG subclasses.

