3.5.5 Pharmacodynamic Per-Protocol Set (PD-PPS)

The PD-PPS is a subset of the SS, consisting of those study participants who had no important protocol deviations potentially affecting the serum concentration of total IgG, as confirmed during a pre-analysis review of the data prior to database lock. Protocol deviations may not necessarily lead to total exclusion of a participant from the PD-PPS but may lead to exclusion of specific data.

Note: Due to the early termination of the study and changes to the analysis, the PD-PPS will not be included in the analysis and the clinical study report.

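### The by-visit total IgG summary in SAP 9.3.1 has no rule for values after rescue IVIg, which is itself IgG

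*SAP*

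**What the plan says.** SAP 9.3 sets the analysis set for all pharmacodynamic endpoints: "The following pharmacodynamic endpoints will be based on the SS", the SS being the Safety Set. For total IgG, SAP 9.3.1 then says: "Total serum IgG concentrations will be summarized and listed on the SS by time point for absolute values, change from Baseline", and adds percent change, overall and by body weight tier. The sentence on IgG subclasses specifies treatment group; the sentence on total IgG does not.

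Protocol 6.4.3 lists "Commercially available IVIg" among the rescue therapies. A rescued participant may go on with study treatment under conditions given there and "should continue to complete all remaining scheduled visits in the Treatment Period". The Schedule of Activities includes repeated IgG samples in that period. Protocol 6.4.2 prohibits IVIg but exempts its use as rescue.

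Protocol 9.1 assigned total IgG to the Pharmacodynamic Per-Protocol Set (PD-PPS), meaning participants with "no important protocol deviations potentially affecting the serum concentration of total IgG", and allowed specific data to be excluded. SAP 3.5.5 says that "the PD-PPS will not be included in the analysis and the clinical study report".

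**The concern.** Most rescue medicines affect IgG indirectly, if at all. IVIg adds the measured substance to the blood. A sample taken in the following weeks therefore shows infused product together with whatever the study drug is doing. Drug exposure may change at the same time, because Protocol 6.4.3 ties the resumption of study treatment after IVIg to the platelet count.

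In the rozanolixizumab arm this makes the fall in IgG look smaller. In the placebo arm it produces a rise that has nothing to do with assignment. The first narrows the contrast between arms and the second widens it, so the net direction depends on who was rescued.

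Total IgG is one of the few exploratory endpoints still summarized after the study was terminated. A reader will use the table to judge how far bi-weekly dosing lowered IgG. Protocol 4.3 reasons from IgG falls of about 50% alongside platelet counts that were not sustained, so a clean IgG summary has some value.

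**Working it through.** The plan attaches no sample size, power or error rate to this summary, so there is no figure to reproduce. The check has two parts.

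**1. Does any rule remove or separate post-IVIg values?**
- SAP 4.2.1 treats rescue as an intercurrent event for efficacy data only. The tables in SAP section 8 likewise concern efficacy endpoints.
- SAP 4.3 stops unscheduled post-dose values from replacing missing scheduled ones. It has nothing to do with rescue.
- SAP 3.5.5 and 3.9 remove the PD-PPS. That set worked through important protocol deviations, and rescue IVIg is permitted, so it is not a deviation in itself.
- SAP 6.6.2 summarizes rescue use but does not link it to IgG.

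No rule was found. That post-IVIg values enter the summary is an inference from using the Safety Set without an exclusion, not SAP wording.

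Two other places in the plan do guard against the same problem. Protocol Table 5-1 requires four weeks free of IVIg before Baseline. SAP Tables 8-2 and 8-3 use platelet data only up to the start of rescue.

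**2. How far could it reach?**

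*Persistence.* SAP 9.2 gives a half-life of 22 days for human IgG. The fraction left after t days is 0.5^(t/22):
- 7 days: 0.80
- 14 days: 0.64
- 28 days: 0.41
- 112 days (16 weeks): 0.03

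One course can thus affect several visits. These fractions assume normal clearance; the study drug speeds up IgG catabolism, so persistence would be shorter in the rozanolixizumab arm.

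*Shift in a visit mean.* SAP 2.3 gives 33 randomized. At 2:1 that is about 22 and 11; the actual split is not stated. Let k be the number with a post-IVIg value at a visit, and d the percentage points by which IVIg raises their change from Baseline. The shift is k × d / n. Neither k nor d is in the documents; d = 25 to 100 is assumed. The reference value for rozanolixizumab is the 52.3% mean fall after a single 15 mg/kg dose in TP0001 (Protocol 2.2).

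| Arm | k of n | Shift (points) | Mean if reference is −52.3% |
|---|---|---|---|
| Rozanolixizumab | 1 of 22 | 25/22 = 1.1 to 100/22 = 4.5 | −51.2% to −47.8% |
| Rozanolixizumab | 4 of 22 | 100/22 = 4.5 to 400/22 = 18.2 | −47.8% to −34.1% |
| Placebo | 1 of 11 | 25/11 = 2.3 to 100/11 = 9.1 | – |
| Placebo | 3 of 11 | 75/11 = 6.8 to 300/11 = 27.3 | – |

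A result in g/L would need an IVIg dose and a distribution volume. Neither is in the documents, so none is given.

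**The case against.** The case for leaving SAP 9.3.1 alone has real substance.

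- **Weight.** Total IgG is exploratory, the study stopped at 33 participants, and no inferential analysis remains. This stands and limits the importance of the point.
- **Other displays.** Total IgG is listed by participant, the pharmacokinetic and antidrug-antibody listings show IgG beside platelet counts, and ITP medications are listed. A patient reader could trace the affected values. This stands, although no listing flags them and the summary would still be mixed. The median, also reported, resists one outlier but not several.
- **Arm imbalance.** Rescue is recommended on low platelet counts, so a reader might infer that IVIg was concentrated in the placebo arm. The documents do not show this. IVIg is one of several options, and Protocol 4.3 reports that platelets were not sustained on the initial regimen in the extension study, so rescue on active treatment is plausible too.
- **The PD-PPS.** A reader might infer that dropping it caused the gap, or that it could never have helped. Neither is supported. It targeted effects on IgG and allowed exclusion of specific data, but through deviations, and the detailed criteria are in a document that is not available here.
- **Excluding values.** The endpoint is defined at each scheduled assessment, so an all-values summary is legitimate. A table restricted to values before IVIg leaves out participants because they needed rescue. It also discards late values when little infused IgG remains (about 3% at 16 weeks). This stands, and is why the restricted table should not replace the full one.

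**Conclusion.** The gap is real. Followed exactly, the plan would combine infused IgG with drug effect in the by-visit total IgG summary, and nothing elsewhere in the plan separates them. The effect on the reported means is unknown and is zero if no one received IVIg. The illustrated shifts rest on assumed k and d and on a 22:11 split.

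Three stronger readings should be resisted. The documents do not show that the IgG results are in fact distorted. No efficacy conclusion changes. The missing mention of treatment group for total IgG does not establish that the arms will be pooled: SAP 3.6 keeps two groups for efficacy and safety data, and 9.3.1 is simply silent.

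One limit on the reading: the analyzed participants were treated under earlier protocol versions. The SAP itself points to Protocol 6.4.3 for rescue, and that text is used here.

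**What to change.** In SAP 9.3.1, present the by-visit total IgG summary (absolute, change, percent change) by treatment group in two displays: one with all values, and one restricted to values before the first IVIg administration. Report the number of post-IVIg values per arm and visit. Flag those values in the IgG listing. Leave the IgG marked-abnormality table (SAP 13.2.2) on all values, since a low IgG matters for safety whatever came before it.

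No new data are needed. Protocol 6.4.3 requires the name, date and dosage of rescue in the eCRF, and SAP 6.6.2 already identifies rescue from the CRF.

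The cost is a few sentences in the SAP, a date filter and one extra table. The restricted display will cover fewer and selected participants at later visits, so it should be read beside the all-values display. If no IVIg was given, the two tables coincide and a footnote is enough.
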